### **7.1.1. Prior Medications**

Prior medications are defined as medications taken and stopped prior to the first dose of study drug. The number and percentage of subjects who took prior medications will be presented by WHO therapeutic drug class and generic drug name.

In addition, a summary of the following will be presented for subjects in the ITT set:

- Antibiotic use 30 days before baseline visit;
- Systemic steroid use 30 days before baseline visit;
- Antifungal medications use 1 year prior to baseline visit.

### **7.1.2. Concomitant Medications**

Concomitant medications are defined as medications started on or before the EOFU visit date with missing stop dates or stop dates after the first dose of study drug.

A summary showing the number and percentage of subjects who took concomitant medications will be presented by WHO therapeutic drug class and generic drug name.

A by-subject listing of prior and concomitant medications will be provided.

### **7.1.3. Rescue Antifungal Medications**

The number and percentage of subjects who took rescue antifungal medication, prior or on TOC visit, after TOC visit but before or on EOFU visit, will be presented for the ITT and mITT sets.

A by-subject listing of rescue antifungal medications will be provided.

## **7.2. Study Treatments**

Please refer to [Section 3.3](#) for the details of the study treatment.

Data related to the study treatment will be presented in a listing.

### **7.2.1. Acute Phase**

#### **7.2.1.1. Exposure of Fluconazole**

The duration of treatment of fluconazole (days) is calculated as (last dose date of fluconazole – first dose date of fluconazole + 1).

The actual fluconazole dose taken across the acute phase will be calculated as the number of fluconazole dispensed minus the number of fluconazole returned. If the fluconazole bottle was not returned, the dose diary data will be considered for the actual fluconazole dose calculation. When subject answered no dose missing, we can assume the actual fluconazole dose is 3 tablets. When subject answered only 1 dose missing, we can assume the actual fluconazole dose is 2 tablets. When subject answered 2 doses missing, we can assume the actual fluconazole dose is 1 tablet. When subject answered 3 doses missing, we can assume the actual fluconazole dose is 0 tablet.

The actual fluconazole dose is missing when subject didn't answer at least one missing dose question.

The duration of treatment of fluconazole, and the actual fluconazole doses will be summarized descriptively for all screened subjects.

All this exposure information of fluconazole will be presented in a listing.

#### **7.2.1.2. Treatment Compliance of Fluconazole**

Treatment compliance of fluconazole is defined as the ratio of the actual fluconazole dose to the planned dose, in terms of percentage. Treatment compliance of fluconazole will be summarized descriptively based on all screened subjects.

Treatment compliance = the actual fluconazole dose / the planned dose (3 tablets) \*100%.

The treatment compliance will be classified as 0%, 33.3%, 66.7%, and 100%. This categorical data will be summarized with the frequency and percentage of subjects based on all screened subjects.

Non-compliance with dose regimen (example 2 tablets taken as a single dose) will be captured based on investigator's review of subject diary.

#### **7.2.2. Prevention of Recurrence Phase**

##### **7.2.2.1. Study Participation Calculation and Extent of Exposure**

The duration of study treatment (days) is calculated as (treatment end date – treatment start date + 1). The treatment start date is the date of first dose of study treatment. For patients who have completed or discontinued study treatment, the treatment end date is the date of last dose of study treatment recorded on end of Study page.

The duration of study participation (days) is calculated as date of Study Completion/Termination recorded on the End of Study page – Inform consent date + 1. If the date of Study Completion/Termination on the End of Study page is missing, or if a subject is lost to follow-up, the latest available visit date will be used.

The cumulative study drug doses taken across the Prevention of Recurrence phase is defined as the total number of study drug dispensed minus the total number of study drug returned. If any of study drug bottle not returned, the missing doses as recorded in the Dosing page of eCRF will be considered for the cumulative study drug doses calculation. For the specified drug dispensation period, the cumulative study doses for that period can be calculated as (6 – the number of times subjects answered dose missing) × 2 tablets each time. For example, when subject answered only 1 dose missing, we can assume the cumulative study drug dose for the specified period is 5 times × 2 tablets each time = 10 tablets. The cumulative study drug dose will set to be missing when subject didn't answer at least one missing dose question.

The duration of study treatment, the duration of study participation, the cumulative study drug doses by treatment will be summarized descriptively.

All this exposure information will be presented in a listing.

#### **7.2.2.2. Treatment Compliance**

Treatment compliance of study drug is defined as the ratio of the actual study dose to the planned dose, in terms of percentage. Treatment compliance will be summarized descriptively.

Treatment compliance = the cumulative study drug dose / the planned dose (24 tablets) \*100%.

The treatment compliance will be classified as <80% and 80% to 100%. This categorical data will be summarized with the frequency and percentage of subjects by treatment group.

Non-compliance with dose regimen (example only 1 tablet taken as a single dose) will be captured based on investigator's review of subject diary.

## 8. Efficacy Analysis

The primary efficacy and secondary efficacy endpoints will be performed on the ITT, mITT and PP sets. The ITT analyses will be considered primary; the mITT and PP analyses will be considered supportive of the primary analyses on the ITT population. The denominator for all percentages will be the number of subjects in that treatment within the analysis set of interest, unless otherwise specified.

### 8.1. Primary Endpoint

The primary efficacy endpoint is defined as the proportion of ITT subjects who have documented Clinical Success (defined as subjects having a TOC evaluation and no Mycologically Proven, Presumed or Suspected Recurrences of VVC) up to Week 24 (TOC).

Clinical success will be assessed according to the following definitions:

- Clinical success: Subjects having a TOC evaluation and no Mycologically Proven, Presumed or Suspected Recurrences of VVC prior to or at the TOC visit.
- Clinical failure: Mycologically Proven, Presumed or Suspected Recurrences of VVC prior to or at the TOC visit. For the subject who early terminated before TOC visit, the subject is considered a clinical failure.

Recurrence of VVC: In this study, Recurrence of VVC will be broken into three categories:

- Mycologically Proven Recurrence: An episode of VVC with a total composite score  $\geq 3$  on the VSS Scale and a culture positive for *Candida* spp. that required antifungal treatment.
- Presumed Recurrence: An episode of VVC with a total composite score  $\geq 3$  on the VSS Scale that required antifungal treatment and for which there is a positive KOH microscopy but no positive fungal culture.
- Suspected Recurrence: An episode of VVC that required treatment with an antifungal agent (including self-administration with over-the-counter antifungals) regardless of VSS composite score but for which there is no mycological evidence of disease, such as a positive KOH microscopy or fungal culture. It also includes an episode of VVC that requires antifungal treatment and have a total VSS composite score lower than 3 regardless of mycological results.

#### 8.1.1. Primary Analysis

The primary efficacy analysis will be performed on the ITT set at the TOC visit and will compare the proportion of subjects, in the treatment and placebo groups, who have documented Clinical Success up to Week 24 (TOC).

The number and percentage of subjects with documented clinical success up to the TOC visit will be presented by treatment group. Meanwhile, the number and percentage of subjects with clinical

failure will be presented by the recurrence categories. A Cochran Mantel Haenszel (CMH) test adjusted for Country and uncontrolled diabetes mellitus (Yes or No) at baseline will be performed to assess the statistical significance of a difference between treatment groups in the primary efficacy analysis. Mathematically stated:

$H_0$ : Clinical Success Rate up to Week 24 (TOC) Oral ibrexafungerp 300-mg dose = Clinical Success Rate up to Week 24 (TOC) Placebo

$H_1$ : Clinical Success Rate up to Week 24 (TOC) Oral ibrexafungerp 300-mg dose  $\neq$  Clinical Success Rate up to Week 24 (TOC) Placebo

The p-value, relative risk and 95% confidence interval (CI) will be presented in the ibrexafungerp 300-mg treatment arm compared to the placebo arm. Subjects who have one or more of the required assessments of potential recurrence not completed prior to or at Week 24 (TOC) visit or subjects who withdraw from the study early will be imputed using the imputation rules described in [Section 4.4.1](#).

A sensitivity analysis using the ITT set will be performed where subjects with the imputed clinical outcome will be removed from the analysis.

Subgroup analyses will be performed in the ITT set depending on BMI category ( $\leq 35$  kg/m^2 or  $>35$  kg/m^2), geographic region (USA and EX-USA), Race (White, Black or African American, Asian, American Indian or Alaska Native, Native Hawaiian or Other Pacific Islander, and Other), Uncontrolled diabetes mellitus (Yes or No), Ethnicity (Hispanic or Latino, Not Hispanic or Latino), Number of recurrent VVC episodes in the prior year ( $<4$  times,  $\geq 4$  times) and Candida species at screening (by Genus species), severity of VVC at screening (2 categorizations of the composite score of the vulvovaginal signs and symptoms at screening will be used to evaluate the severity of VVC at screening:  $<7$ ,  $\geq 7$  and '4 - 7', '8 - 12', and ' $\geq 13$ ').

The same inferential analysis employing the same methods as for the primary analysis will be performed for the mITT set and PP set to assess clinical success rate up to the Week 24 (TOC). Subjects whose results are missing at Week 24 (TOC) and subjects who withdraw from the study early will be imputed using the imputation rules described in [Section 4.4.1](#). No adjustment of type I error will be performed as these analyses are considered supportive to the primary analysis.

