10.1.1.3 Prevention of Recurrence Phase (Day 1 [Baseline] through Week 36 [EOFU])

10.1.1.3.1 Study Treatment Period (Day 1 [Baseline] through Week 24 [TOC])

Baseline (Day 1)

On Day 1, subjects will return their open-label fluconazole supplies. Treatment compliance will be evaluated, and subject diaries will be collected and reviewed. Vulvovaginal samples will be collected for fungal culture and pH. The investigator and the subject will rate the signs and symptoms of infection, respectively, on the VSS Scale. The subject's QOL questionnaires will be administered. The results of the vaginal culture collected at Screening will be reviewed.

Subjects with a culture-confirmed *Candida* spp. infection from the sample collected at Screening who achieve a significant resolution of their vulvovaginal signs and symptoms (total composite score ≤ 2 on the VSS Scale) and continue to meet all study eligibility criteria at Baseline (Day 1) will continue to the Prevention of Recurrence Phase, where they will be randomized at a 1:1 ratio to receive one of the following two study treatments in a double-blind manner:

- Oral ibrexafungerp administered as a single-day treatment repeated every 4 weeks (28 days [± 3]) for a total of 6 single-day treatments (Baseline [Day 1], Week 4, Week 8, Week 12, Week 16 and Week 20). Each single-day treatment will consist of two doses of 300 mg each given 12 (± 4) hours apart (total single-day dose = 600 mg).
- Matching oral placebo administered as a single-day treatment repeated every 4 weeks (28 days [± 3]) for a total of 6 single-day treatments (Baseline [Day 1], Week 4, Week 8, Week

12, Week 16 and Week 20). Each single-day treatment will consist of two doses of placebo given 12 (± 4) hours apart.

Subjects will receive their first dose of study drug at the site and will be dispensed double-blind study drug and subject diaries, where they will rate their vulvovaginal symptoms on a weekly basis and at the time of each visit to the site, and will record dosing details, AEs and concomitant medication use during the study. Safety procedures (abbreviated physical exam, vital signs, AE collection and urine pregnancy test) will be conducted.

Subjects who do not have a culture-confirmed *Candida* spp. infection at Screening, do not achieve a significant resolution of their signs and symptoms at Baseline (Day 1) and/or do not continue to meet all eligibility criteria will be discontinued from the study.

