18.1 Sample Size Determination

The primary endpoint of the study is the percentage of subjects with documented Clinical Success up to TOC (Week 24). Assuming response rates of 65% and 43% for ibrexafungerp and placebo, respectively; 90% power; and an alpha level of 0.05, approximately 240 subjects randomized at a 1:1 ratio are needed to declare a difference between ibrexafungerp and placebo at Week 24 based on Fisher's Exact test.

In order to be randomized, a subject should have achieved the proposed significant resolution of signs and symptoms (total composite score ≤ 2 on the VSS Scale) after receiving fluconazole therapy for an acute episode and have a positive culture for *Candida* spp. from the sample collected at Screening. It is estimated that approximately 320 subjects will need to enter the Acute Phase to provide 240 subjects randomized to the Prevention of Recurrence Phase. Enrollment into the Acute Phase will be discontinued when approximately 240 subjects have been randomized.

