#### 4. General Statistical Considerations

Continuous data will be described using descriptive statistics (i.e. n, mean, standard deviation (SD), median, minimum, and maximum). Categorical data will be described using the subject count and percentage in each category. For the summary statistics of all numerical variables unless otherwise specified, minimum and maximum will be displayed to the same level of precision as reported. Mean and median will be displayed to one level of precision greater than the data collected. Standard deviation / standard error will be displayed to two levels of precision greater than the data collected. P-values will be rounded to three decimal places. If a p-value is less than 0.001 it will be reported as “<0.001.” If a p-value is greater than 0.999 it will be reported as “>0.999.” Data will be displayed in all listings sorted by treatment group.

Subjects will be identified in the listings by the subject identification number concatenated with the investigator number.

When count data are presented, the percentage will be suppressed when the count is zero in order to draw attention to the non-zero counts. A row denoted “Missing” will be included in count tabulations where specified on the shells to account for dropouts and missing values. The denominator for all percentages will be the number of subjects in that treatment within the analysis set of interest, unless otherwise specified.

Unless otherwise specified, baseline will be defined as the last non-missing assessment prior to or on the date (and time if appropriate) of the first dose of study drug. Change from baseline is defined as post-baseline value – baseline value.

The study day will be calculated as follows:

If the assessment date occurs on or after the date of the first dose of study drug:

$$\text{Study day} = \text{assessment date} - \text{first dose date} + 1.$$

If the date of interest occurs before the date of the first dose of study drug:

$$\text{Study day} = \text{assessment date} - \text{first dose date}$$

There is no study day 0.

All analyses will be conducted using SAS Version 9.3 or higher. All statistical tests will be two-sided and interpreted at a 5% significance level.

This statistical analysis plan is created for the main study. Regarding the detailed description of the statistical analysis of the nested sub-study, please refer to the [Appendix 4](#).

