#### **4.3. Analysis Set**

Intent-to-Treat (ITT) Set: All randomized subjects who received at least one dose of study drug (ibrexafungerp or placebo).

Modified Intent-to-Treat (mITT) Set: All randomized subjects who received at least one dose of study drug (ibrexafungerp or placebo), who have a confirmed mycological culture for yeast at Screening and a negative culture for yeast at Baseline (Day 1).

Per-Protocol (PP) Set: All mITT subjects who did not have major protocol deviations likely to affect study efficacy and who have available data at the TOC visit. Note that subjects who discontinue due to a study-drug-related AE will be classified as failures for the analyses of efficacy under the PP population.

Safety Set (SS): All randomized subjects who received at least one dose of study drug (ibrexafungerp or placebo) and who have at least one post-baseline evaluation.

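### The primary CMH test is valid but leaves out the Day 1 culture result, a plausibly prognostic baseline variable already collected; adding it is a cheap, modest gain

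*SAP*

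**What the plan says.** - **Primary test.** SAP 8.1.1, on the ITT set: "A Cochran Mantel Haenszel (CMH) test adjusted for Country and uncontrolled diabetes mellitus (Yes or No) at baseline will be performed". A p-value, relative risk and 95% CI are reported.
- **Origin of the factors.** SAP 4.2 stratifies randomisation by uncontrolled diabetes (A1C of 8.00% or more) and by USA versus Ex-USA. SAP 11 adds diabetes because it is a stratification factor, and replaces site with Country. SAP 6.1 lists four countries.
- **Day 1 culture is taken.** Protocol 10.1.1.3.1, for the Baseline visit: "Vulvovaginal samples will be collected for fungal culture and pH". This step comes before randomisation in the visit description, and the pH from the same step is an entry criterion. Protocol 14.7 has the culture processed centrally.
- **A negative Day 1 culture is not an entry condition.** Protocol 11.1, criterion 3, asks for a positive Screening culture and a VSS score of 2 or less at Day 1.
- **Where the result is used.** SAP 4.3 restricts mITT to women "who have a confirmed mycological culture for yeast at Screening and a negative culture for yeast at Baseline (Day 1"), and PP is a subset of mITT. SAP 8.2.2 compares culture negativity between arms at Baseline with the primary method. SAP 6.2 tabulates Candida species at baseline. Day 1 culture is neither in the primary CMH nor in the subgroup list of SAP 8.1.1.

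**The concern.** A woman who still carries yeast on Day 1 may well recur more often than one who has cleared it. The background sections (Protocol 7.1, SAP 1) attribute recurrence after fluconazole to low numbers of yeast that survive treatment, and a Mycologically Proven Recurrence itself needs a positive culture. If the result predicts outcome, a primary test that ignores it gives up some power. It also lets a chance difference between arms in the share positive pass into the primary estimate. Separately, the ITT and mITT results could differ with nothing in the plan to show why, because no efficacy result is planned for Day 1 culture-positive women.

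**Working it through.** **1. The plan's own figure.** Protocol 18.1 arrives at about 240 women in two equal arms, sized with Fisher's test, from these inputs: "Assuming response rates of 65% and 43% for ibrexafungerp and placebo, respectively; 90% power; and an alpha level of 0.05". SAP 4 makes tests two-sided at 5%. Exact enumeration of Fisher's test at 120 per arm gives 90.9% power, so the stated design reproduces. The large-sample test of two proportions at 120 per arm gives 93.3%. A CMH test behaves more like the latter, so the planned test starts at about 92-93%.

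**2. Inputs the documents do not give (assumed).**
- Share culture-positive on Day 1, q: 15% to 35%.
- Deficit in success among culture-positive women, d: 20 to 40 points, the same in both arms.
- Uncontrolled diabetes: 3%. Country shares: 55/15/15/15%. Neither factor is given an effect on outcome.

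The overall rates are held at 65% and 43%. Success is p + d x q in culture-negative women and p - d x (1 - q) in culture-positive women. Placebo example at q = 0.25, d = 0.30: 0.43 + 0.075 = 50.5% and 0.43 - 0.225 = 20.5%.

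**3. Power at 120 per arm** (40,000 simulated trials per row; standard error about 0.13 points).

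| q, d | Country x diabetes (planned, 8 cells) | Country x diabetes x culture (16 cells) | Region x diabetes x culture (8 cells) |
|---|---|---|---|
| 15%, 20 points | 92.6% | 92.5% | 93.0% |
| 25%, 30 points | 92.6% | 93.9% | 94.4% |
| 35%, 40 points | 92.6% | 95.7% | 96.1% |
| 25%, no effect | 92.7% | 92.1% | 92.7% |

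The 8-cell version gains about 0.5, 1.8 and 3.5 points, and nothing if culture is not prognostic. The 16-cell version is slightly worse throughout because it is sparser. At 3% diabetes there are 0.03 x 240, or about 7, diabetic women to spread over eight cells. A separate run with culture as the only stratifier, 10-40% positive and odds ratios of 0.5 to 0.1, gave gains of 0.6 to 5.1 points. The upper end needs an odds ratio near 0.1.

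**4. Type I error.** With equal rates of 43% or 54% in both arms, the 8-cell culture version rejects in 4.8% to 5.2% of trials, the same as the planned test within simulation error.

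**5. Chance imbalance.** The SD of the between-arm difference in share positive is sqrt(2q(1 - q)/120). A one-SD imbalance shifts the unadjusted risk difference by that SD times d.
- q = 0.15: SD 4.6 points; x 0.20 = 0.9 points.
- q = 0.25: SD 5.6 points; x 0.30 = 1.7 points.
- q = 0.35: SD 6.2 points; x 0.40 = 2.5 points.

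The assumed effect is 65 - 43 = 22 points. The plan reports a relative risk, so on that scale, splitting the shift evenly between arms: the design value is 65/43 = 1.51. A 0.9-point shift gives 65.46/42.54 = 1.54 or 64.54/43.46 = 1.49. A 2.5-point shift gives 66.23/41.77 = 1.59 or 63.77/44.23 = 1.44.

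**The case against.** The strongest case against is that nothing is wrong. Adjusting for the factors used at randomisation is standard, leaving out a covariate does not inflate type I error, and the test already exceeds its 90% target. All of that stands: this is an efficiency option.

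Four stronger readings are tempting, and the documents do not support them.
- *Day 1 culture is a strong predictor and uncontrolled diabetes is rare.* Neither has a figure. The first rests on a mechanistic rationale, the second only on the requirement for good general health. Diabetes also belongs in the test because it stratified randomisation, however common it proves to be.
- *An imbalance would go unseen and uncorrected.* SAP 8.2.2 shows culture status by arm at Baseline. The supportive mITT and PP analyses remove any imbalance by restricting to culture-negative women. It stays uncorrected only in the primary ITT test.
- *Adjustment would explain a gap between ITT and mITT.* It gives one common estimate across culture states. Only a subgroup result would show whether the effect differs between them.
- *Every randomised woman has a usable result.* Collection is scheduled and processing is central, so results can be missing, and a rule is needed.

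A further objection stands in part: region in place of Country departs from a documented choice in SAP 11. If outcome differs among Bulgaria, Russia and Poland, some precision is lost. The simulation gives Country no effect and so does not measure that loss.

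**Conclusion.** The point holds as a modest improvement to a valid primary analysis. Over the assumed range (15-35% positive, success 20-40 points lower), adding Day 1 culture gains roughly 0 to 4 points of power on about 92-93%. Type I error stays near 5%, and a one-SD imbalance shift of about 1 to 2.5 points in the risk difference is removed. With no prognostic effect the cost in power is essentially nil. The size rests entirely on the assumed positive share and deficit; the share can be checked on pooled, blinded data. The missing subgroup matters at least as much as the power, since the plan would otherwise show no efficacy result in the women whom mITT excludes for a positive Day 1 culture.

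**What to change.** Before unblinding, in SAP 8.1.1:

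1. Make the primary CMH strata region (USA/Ex-USA) x uncontrolled diabetes x Day 1 culture (negative/positive). This is 2 x 2 x 2 = 8 cells, as many as now, and keeps both actual randomisation factors.
2. Count a missing Day 1 culture as positive. This follows SAP 4.4.1 and 8.2.2, which treat missing mycology as persistence, and matches mITT, which requires a negative result.
3. Keep the Country x diabetes CMH as a sensitivity analysis.
4. Add Day 1 culture (positive/negative) to the ITT subgroup list and show it beside mITT.
5. Record the change and its reason in SAP 11.

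If the sponsor prefers not to alter the primary test, the minimum is to pre-specify the culture-adjusted ITT analysis as supportive, plus item 4. The cost is SAP wording and programming, with no new data. The downsides are that Country gives way to region in the primary strata and that the diabetic cells will be small.
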